## 8 STUDY ASSESSMENTS AND PROCEDURES

### 8.1 EFFICACY ASSESSMENTS

#### Study Procedures:

**General overview:** All subjects will complete consenting and then a candidacy evaluation to determine if they meet study criteria. Once they meet criteria, they will be scheduled for a baseline re-assessment. Following the baseline assessment, they will be randomly assigned to a study arm (treatment or sham) and then training on how to use the device before taking it home. They will take home the device on the same day they complete the baseline assessment. Follow up assessments will take place weekly, and assessments completed at the weekly session are noted below. Additionally, some measures will only be completed at the beginning or end of the active treatment or sham conditions and following washout of active or sham treatment.

#### Specific procedures:

1. Audiologic case history:
  - a. Will be administered to each enrolled subject at the initial appointment in the study (candidacy evaluation) following completion of the consent form. This questionnaire includes basic information regarding the patient's audiologic and medical history. This will be administered by the study team audiologist or other trained technician. This is not repeated at any other point in the study unless the patient reports a change in audiologic history.
2. Otologic examination and medical case history:
  - a. Will be administered to each enrolled subject at the initial appointment in the study (candidacy evaluation) following completion of the consent form. This questionnaire includes basic information regarding the patient's otologic and medical history. This will be administered by a physician/otologist on the study team. This is not repeated at any other point in the study unless the patient reports a change in otologic or medical history.
  - b. If an otologic examination warrants further medical evaluation or intervention (standard of care) then an appropriate recommendation will be made by a physician study team member. If a subject is required to seek further medical evaluation, he/she will not be able to participate in the trial until he/she has been properly evaluated and has provided test results or a letter from a physician indicating as such. These costs are not covered by the study.
  - c. If mental health issues are identified during the screening process, the screening physician will refer the subject back to their primary care physician for further evaluation and/or follow-up.
3. Tinnitus modulation checklist
  - a. Will be administered to each enrolled subject at the initial appointment in the study (candidacy evaluation) following completion of the consent form. This questionnaire involves a study team member asking the subject to perform a series of movements and then requiring that the subject subjectively report if a given movement caused a change in tinnitus. Only subjects who are able to modulate their tinnitus with one of the somatic maneuvers will be eligible to participate in the study. This will be assessed at the candidacy evaluation, and then according to the Schedule of Events (Section 1.3).
4. Audiometric assessment:
  - a. A basic audiometric assessment will be performed at the initial appointment in the study (candidacy evaluation) following completion of the consent form and then according to the Schedule of Events (Section 1.3). The basic audiometric assessment follows standard clinic procedures in both ears. This includes a behavioral audiogram using air-conduction (250-8000 Hz) and bone conduction (250-4000 Hz) stimuli presented through calibrated headphones or bone conduction transducer, respectively. Speech detection thresholds will also be assessed to determine reliability. This data will be assessed to determine if a subject meets eligibility criteria for hearing loss. It will also be reassessed bi-weekly to determine if hearing thresholds worsen during each treatment arm as outlined in the stopping criteria.

5. TinnTester:

- a. Objective tinnitus loudness (TinnTester): This assessment is described in Section 3 of this document. It will be assessed at the baseline evaluation, and then according to the Schedule of Events (Section 1.3).
- b. Objective tinnitus bandwidth (TinnTester): This assessment is described in Section 3 of this document. It will be assessed at the baseline evaluation, and then according to the Schedule of Events (Section 1.3).
- c. Sound tolerance level (TinnTester): This assessment is described in Section 3 of this document. It will be assessed at the baseline evaluation, and then according to the Schedule of Events (Section 1.3).

6. Minimum Masking Level:

- a. This assessment is described in Section 3 of this document. It will be assessed at the baseline evaluation, and then according to the Schedule of Events (Section 1.3).

7. Tinnitus Function Index (TFI)

- a. This assessment is described in Section 3 of this document. It will be assessed at the candidacy evaluation, and then according to the Schedule of Events (Section 1.3).

8. Tinnitus Handicap Inventory (THI)

- a. This assessment is described in Section 3 of this document. It will be assessed at the baseline evaluation, and then according to the Schedule of Events (Section 1.3).

9. Tinnitus Hearing Survey (THS):

- a. This assessment is described in Section 3 of this document. It will be assessed at the baseline evaluation and then according to the Schedule of Events (Section 1.3)

## 8.2 SAFETY AND OTHER ASSESSMENTS

Subject participation will entail weekly visits to the lab for detailed assessments. The weekly visits to the lab will ensure that subjects are using the devices correctly and safely. The weekly visits also allow us to monitor changes in the tinnitus percept in response to device use or washout from the treatment. The regular assessments also provide us with the opportunity to detect any adverse events as soon as possible, should any occur.

Currently, there is no standard treatment for tinnitus that has been shown to be broadly effective at treating tinnitus, so participation in the study will not interfere with standard clinical intervention. Subjects will be informed during the consenting process that there are alternative methods of treatment such as sound therapy that they may find beneficial, and

referred to their primary care physician for referrals should they elect to pursue that form of treatment.

Regular assessments will also allow for swift intervention should a subject experience an adverse event or worsening of symptoms. We will stop the study should 10% of subjects show a persistent worsening in their symptoms. A subject's participation in the study will be discontinued following **both** 1) an increase of 16 or more points in TFI, **and** 2) an average increase of 12 dB in TinnTester compared to baseline, for two consecutive weekly measures. Both measures are our primary outcome measures. Using both criteria for determining discontinuation is critical as the tinntester measures tinnitus loudness, which reflects the circuitry changes identified in our preclinical studies. TFI is also important for the human study as it gauges the subject's subjective response to their tinnitus. However, TFI can also reflect outside life stressors unrelated to the treatment and could result in a subject's discontinuation for reasons unrelated to the treatment. A subject's participation can also be discontinued even if the criteria above is not met, but the subject feels their tinnitus is worse.

This study does not require and will not use a Data Safety Monitoring Board (DSMB) because it is not a multi-site study. However, because it is a double-blinded, cross-over study we will implement and an Independent Safety Monitor (ISM) for data monitoring purposes. *The ISM will be clinical research monitor of the Michigan Institute for Clinical & Health Research (MICHR) who can provide independent monitoring of the human data. The ISM will be responsible for overseeing and monitoring the enrollment data, safety data and data integrity. The ISM will be unblinded to the intervention assignment for each subject. The ISM will be independent of the investigation. He/she will not be a collaborator, co-author, supervisor, mentor/mentee, research lab member, or member of the institutional department within the last three years. He/she will not have any professional or financial conflict of interest.*

The PI ([name]) will comply with the NIMH Reportable Events policy. The intervention will continue for each subject so long as adverse events do not occur for that individual. The ISM will monitor data and review safety data. If adverse events related to the study (definitely related, probably related, or potentially related) do occur, they will be reported to the IRB within 14 days and will be reported to the PI immediately. All other adverse events will be reported annually at the time of IRB renewal. This study uses a non-invasive device. We will use strictly calibrated instruments to ensure that both acoustic and electrical stimulation are being delivered at safe levels for each subject. However, specific stopping rules will be identified for each subject to ensure patient safety. For each subject, data for the TFI, THI, TinnTester, and audiologic examinations will be examined on a weekly basis (following weekly testing for each subject) for tinnitus assessments to determine if either measures indicate a statistically significant increase in tinnitus or decrease in hearing (in reference to the individual's baseline measure). This metric will be monitored by the ISM. If tinnitus is found to increase or hearing loss worsen, then the subject will not continue in the study regardless of which arm (active or sham) in which the subject is enrolled. Furthermore, if the subject subjectively reports increase in tinnitus or worsening of hearing, without a significant change in

any of the subjective or objective measures, and he/she wishes to discontinue participation in the study then he/she will withdraw from the study.

The study protocol and treatment device includes transmission of both acoustic and electric (transdermal) stimulation. For both stimulation types, stimuli are strictly controlled as to not cause harm or discomfort for the subject. For acoustic stimulation, the intensity is set at 30 dB SL (as determined by the subject's pure tone average), with each sound presented for 10 ms with 2 ms linear rise and fall times. This intensity level is expected to be within a comfortable listening range for each subject (based on clinical experience and previous research trial data). For the electric stimulation, the electrodes are positioned on the cheek overlying the trigeminal ganglion, the juncture of the temporomandibular joint or on the neck at overlying cervical nerves, C1 or C2, depending on which region modulates the tinnitus (based on the modulation maneuver checklist). Electrical stimulation levels are just below the threshold of muscular contraction (1-3 mA) as in the animal studies, limited by subject's comfort. This level of electric stimulation is typically one that initially results in a small, comfortable tingling at the stimulation site upon initial activation. However, based on our previous research trial subjects often report that electric stimulation cannot be detected within a few minutes of initial stimulation. This low level of electrical stimulation causes no harm to the subject. The sham protocol uses the same electrical and acoustic levels but the bimodal interval is wider than that used to induce STDP (>100 ms). Based on work in the animal, we expect that using wider bimodal intervals will cause no harm to the subject.

The subject will be consented by one of the study team members at the initial candidacy appointment. Consenting will take place in the Human lab on the 2nd floor of Med. Sci. I. at the University of Michigan, or online via HIPAA approved Zoom videoconferencing application. Patients will be seated in a comfortable chair in a semi-private room and be allowed to ask questions regarding the study. Tinnitus assessments will take place in a private, double-walled sound booth. Fitting of the device will take place in a semi-private laboratory room. Medical evaluations will be completed by [name] or [name] in a private examination room at the Otology Clinic at the University of Michigan, in the Human Lab on the 2nd floor of Med. Sci. I, or online via HIPAA approved Zoom videoconferencing application. Any incidental findings will be reported to the subject and [name] or [name] will make the appropriate medical referrals if necessary.

We will keep all subject information secure. All data will be collected and tracked electronically. Data will be stored, using a secure data network system supported by the Michigan Institute for Clinical and Health Research (MICHR). Subjects will communicate with research team members by phone or a secure web portal. Data will be coded, password protected and encrypted.

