## 7 STUDY INTERVENTION DISCONTINUATION AND PARTICIPANT DISCONTINUATION/WITHDRAWAL

### 7.1 DISCONTINUATION OF STUDY INTERVENTION

This study uses a non-invasive device. We will use strictly calibrated instruments to ensure that both acoustic and electrical stimulation are being delivered at safe levels for each subject. However, specific stopping rules will be identified for each subject to ensure patient safety. For each subject, data for the TFI, THI, and TinnTester will be examined on a weekly basis (following weekly testing for each subject) for tinnitus assessments. Additionally, audiometric criteria will be assessed at least every 6 weeks (please see schedule of events) to monitor hearing status. Audiometric criteria will be evaluated during the interim if a subject reports concern for a change in hearing ability. This metric will be monitored by the ISM. If tinnitus is found to statistically, significantly increase according to aggregated mean baseline, then the subject will not continue in the study regardless of which arm (active or sham) in which the subject is enrolled. Furthermore, if the subject subjectively reports increase in tinnitus or worsening of hearing, without a significant change in any of the subjective or objective measures, and he/she wishes to discontinue participation in the study then he/she will withdraw from the study.

A subject's participation in the study will be discontinued following **both** 1) an increase of 16 or more points in TFI, **and** 2) an average increase of 12 dB in TinnTester compared to baseline, for two consecutive weekly measures. Both measures are our primary outcome measures. Using both criteria for determining discontinuation is critical as the tinntester measures tinnitus loudness, which reflects the circuitry changes identified in our preclinical studies. TFI is also important for the human study as it gauges the subject's subjective response to their tinnitus. However, TFI can also reflect outside life stressors unrelated to the treatment and could result in a subject's discontinuation for reasons unrelated to the treatment.

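### Sections 7.1 and 8.2 state conflicting mandatory rules for discontinuing an individual subject

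*Combined protocol and SAP*

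**What the plan says.** **Numeric rule (7.1, second paragraph; repeated in 8.2).** Participation ends after both "an increase of 16 or more points in TFI" and "an average increase of 12 dB in TinnTester compared to baseline, for two consecutive weekly measures". The plan adds: "Using both criteria for determining discontinuation is critical". Its reason is that TFI alone can respond to life stressors that have nothing to do with treatment.

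**Significance wording in 7.1, first paragraph.** "If tinnitus is found to statistically, significantly increase according to aggregated mean baseline, then the subject will not continue in the study". The test, the size of change and the aggregated baseline are not defined.

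**Significance wording later in 8.2.** "For each subject, data for the TFI, THI, TinnTester, and audiologic examinations will be examined on a weekly basis", and the purpose is "to determine if either measures indicate a statistically significant increase in tinnitus or decrease in hearing (in reference to the individual's baseline measure"). The consequence follows: "If tinnitus is found to increase or hearing loss worsen, then the subject will not continue in the study". No test, persistence condition or hearing threshold is given.

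**Audiometry for this purpose.** It is at least six-weekly in 7.1, bi-weekly in 8.1 (audiometric assessment) and weekly in 8.2.

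**Study-level stop (8.2).** "We will stop the study should 10% of subjects show a persistent worsening in their symptoms". Persistent worsening, the denominator and the time of assessment are not defined.

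**What happens after removal.** Section 7.2 replaces subjects who are withdrawn or discontinued after receiving the intervention. Section 9.3 handles missing data and losses to follow-up by last observation carried forward.

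**The concern.** The passages are written as mandatory, yet they differ in the measures used, in whether one measure is enough, in the reference baseline, in the threshold and in persistence. Staff who follow different paragraphs would treat the same subject differently.

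The statistical stake is that removal is triggered by the primary outcomes themselves. A rule that acts on a single high reading removes some subjects at a chance peak, and last observation carried forward then makes that peak the analysed value. A subject removed during Arm 1 also contributes no observed data from Arm 2, and the replacement is a different person. The rule in force therefore decides how much data is missing, and which data.

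The safety stake runs in both directions: a subject whom one passage would remove may continue under another. The study-level stop also counts worsening without saying what worsening is.

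**Working it through.** **Step 1. The passages side by side.**

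| Feature | Numeric rule (7.1, 8.2) | Significance wording, 7.1 | Significance wording, 8.2 |
|---|---|---|---|
| Measures | TFI and TinnTester | Tinnitus; TFI, THI and TinnTester reviewed weekly | TFI, THI, TinnTester, audiologic examination |
| Combination | Both required | Not stated | Either suffices |
| Baseline | Baseline | Aggregated mean baseline | Individual's own baseline |
| Size | 16 points and 12 dB | Significance, test not given | Significance, test not given |
| Persistence | Two consecutive weekly measures | None | None |
| Hearing | Not included | Monitored, but not in the removal sentence | Worsening removes; no threshold |

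**Step 2. Apply them to the same subject.**
- *TFI up 16 points in two consecutive weeks, judged significant; TinnTester unchanged.* The numeric rule is not met, because it needs both parts. Under 8.2, one measure suffices and the subject leaves.
- *Hearing worse, tinnitus unchanged.* The subject leaves under 8.2. Neither the numeric rule nor the 7.1 removal sentence covers the case.

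This establishes the conflict and needs no calculation.

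**Step 3. How far apart the rules could be (illustration only).** The documents give no chance-removal rate, so there is no figure to reproduce.

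Assumptions for the significance wording:
- 0.025 per look in the worsening direction. This is half of the two-sided 0.05 in 9.4, which the plan does not tie to individual removal.
- 12 weekly looks: two 6-week device periods, or one device period and its washout before the second baseline.
- No persistence requirement.
- A stable subject with normal measurement error and one baseline reused at every look.
- Correlation between measures 0.3 or 0.7; week-to-week autocorrelation 0 or 0.5.
- Baseline from one reading or the mean of four.

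Results over 12 looks:
- One measure, independent looks: 1 - 0.975^12 = 26%. Simulated with the shared baseline: 14-22%.
- Three measures, independent: 1 - 0.975^(12 × 3) = 1 - 0.975^36 = 60%. Simulated with correlation and the shared baseline: 26-50%.

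The independence figures are upper bounds, because reusing one baseline makes the looks dependent.

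For the numeric rule, the assumed SDs of change run from 8 TFI points and 6 dB to 16 points and 12 dB, with correlation 0 or 0.3 and autocorrelation 0 or 0.5. Simulated over 12 looks:
- SDs 8 and 6: 0.02-0.3%.
- SDs 13 and 8: 0.6-3.2%.
- SDs 16 and 12: 2.6-9.1%.

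**Step 4. What the illustration depends on.** If the three-measure significance check had to be exceeded in two consecutive weeks, chance removal would be about 6-13% (correlation 0.4, autocorrelation 0 to 0.5, one or two baseline readings). The missing persistence condition therefore accounts for much of the gap.

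**The case against.** **The passages can be reconciled.** Sections 7.1 and 8.2 both say that specific stopping rules will be identified for each subject, and the numeric rule could be that specification. The amendment history describes the change to these sections as a clarification of the TFI and TinnTester criteria. This is plausible, but no sentence says so. The numeric rule also leaves out THI and hearing, which 8.2 monitors, and the significance wording remains in the current text.

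**Both could be sufficient conditions, applied whichever comes first.** Then the numeric rule would no longer prevent removal on TFI alone, which is the reason the plan gives for requiring both parts. The subject's own wish to leave is a separate route in both sections and does not explain the difference.

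**A reader might infer three distinct rules, the loosest removing a subject for any rise at all.** The documents do not support that. The sentence in 8.2 follows a reference to a statistically significant change, and the next sentence deals with subjects who have no significant change. The natural reading is that the increase must be significant. The two significance statements are then close relatives that differ in baseline, measures and hearing, so there are nearer two rules than three.

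**The removal rates are not facts of this plan.** This stands. Test, alpha, error variance and looks are all assumed. The rates also describe only removal of stable subjects, not failure to remove subjects who truly worsen, so they do not favour either rule.

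**Conclusion.** The conflict stands on the text alone: mandatory passages give opposite answers for a subject with a significant rise on one measure, and nothing ranks them. It should be resolved, because removal acts on primary outcomes and feeds carried-forward data and replacement.

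The size is conditional. With weekly one-sided 2.5% checks and no persistence, chance removal over 12 looks is about 14-22% on one measure and 26-50% on three, against about 0.02-9% under the numeric rule across the assumed SDs. The ranges show that the choice of passage could matter a great deal; they do not predict what will happen.

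Two stronger conclusions might be drawn and are not supported. One is that the looser wording would in fact remove a large share of stable subjects; the plan specifies no test from which that follows. The other is a probability that chance flags trigger the 10% study stop. The plan gives no denominator, start of monitoring or definition of persistence, so such a probability would mostly reflect the reviewer's assumptions. What can be said is that 10% means 5 subjects out of 50 or 10 out of 100, and the plan does not say which applies.

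**What to change.** 1. Reconcile 7.1, 8.1 (audiometric assessment) and 8.2 so that the tinnitus criteria, the hearing criteria and the audiometry frequency are stated once and identically, in agreement with the Schedule of Activities. Hearing should keep its own explicit statement and not be lost in the merger.
2. State whether the numeric rule defines or replaces the significance wording. If any significance wording stays, give the test, the reference baseline, the measures, whether one suffices and any persistence condition.
3. For the 10% study stop, define persistent worsening, the denominator and the time of assessment.

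Which rule to adopt is for the investigators, the safety monitor and the IRB; this point takes no position on it.

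The cost is protocol wording plus the IRB approval that the Statement of Compliance requires before a change takes effect. No new data or visits are needed for the tinnitus wording. Any effect on audiometry visits depends on the frequency chosen.
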